## 4.2 METHOD OF TREATMENT ASSIGNMENT AND BLINDING

### 4.2.1 Treatment Assignment

This is a three-arm randomized study. After initial written informed consent has been obtained, all screening procedures and assessments have been completed, and eligibility has been established for a patient, the study site will obtain the patient's treatment assignment from an interactive voice or web-based response system (IxRS).

Patients will be randomly assigned to one of three treatment arms: the vixarelimab [REDACTED] arm, vixarelimab [REDACTED] arm, or placebo arm in a [REDACTED] ratio. Randomization will occur through use of a permuted-block randomization method to ensure a [REDACTED]. Randomization will be stratified by advanced or conventional failure and baseline mMS [REDACTED]. During the optional ATE period, patients assigned to the vixarelimab [REDACTED] arm or the vixarelimab [REDACTED] arm during the induction period will continue on the randomized treatment assignment; patients treated with placebo during the induction period will receive vixarelimab [REDACTED] (see Section 3.1.1 for further details).

### 4.2.2 Blinding

Study site personnel and patients will be blinded to treatment assignment *until database lock*. The Sponsor and its agents will also be blinded to treatment assignment *until the execution of the primary analyses*, with the exception of a *limited set of individuals who are not directly involved with study conduct and* require access to patient treatment assignments to fulfill their job roles during a clinical trial. These roles include the unblinding group responsible, clinical supply chain managers, sample handling staff, operational assay group personnel, IxRS service provider, and IMC members.

While PK and immunogenicity samples must be collected from patients assigned to the placebo arm to maintain the blinding of treatment assignment, PK and ADA assay results for these patients are generally not needed for the safe conduct or proper interpretation of the study data. Laboratories responsible for performing study drug PK and ADA assays will be unblinded to patient treatment assignments to identify appropriate samples for analysis. PK samples from patients assigned to the placebo arm will not be analyzed for study drug PK concentration except by request (e.g., to

evaluate a possible error in dosing). Baseline immunogenicity samples will be analyzed for all patients. Postbaseline immunogenicity samples from patients assigned to the placebo arm will not be analyzed for ADAs except by request.

If unblinding *becomes necessary because of* a medical emergency (e.g., serious adverse event for which management might be affected by knowledge of *the participant's* treatment assignment), the investigator will be able to break the treatment code *via* the IxRS. The investigator is not required to contact the Medical Monitor prior to breaking the treatment code *in an emergency situation*. However, the Medical Monitor *should be informed* that the treatment code has been broken.

*The investigator will also be able to break the treatment code to determine the suitability of subsequent medical care for a participant. However, approval must be obtained from the Sponsor Medical Monitor if the investigator wants to break the treatment code to determine a participant's eligibility for a subsequent clinical trial testing investigational medicinal products or procedures. The investigator must contact the Sponsor Medical Monitor prior to breaking the treatment code for any reason other than a medical emergency. The investigator should document and provide an explanation for any non-emergency unblinding.*

As per health authority reporting requirements, the Sponsor's Drug Safety representative will break the treatment code for all serious, unexpected suspected adverse reactions that are considered by the investigator or Sponsor to be related to drugs listed in Section 5.7). The investigator, patient, and Sponsor personnel, with the exception of the Drug Safety representative and personnel who must have access to patient treatment assignments to fulfill their roles (as defined above), will remain blinded to treatment assignment.

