### **3. STUDY DESIGN**

#### **3.1 DESCRIPTION OF THE STUDY**

##### **3.1.1 Overview of Study Design**

This is a Phase II, multicenter, randomized, parallel-group, double-blind, placebo-controlled, dose-ranging study to evaluate the efficacy, safety, and pharmacokinetics of vixarelimab compared with placebo in patients with active moderate to severe UC, including 1) patients who have demonstrated inadequate response to, loss of response to, or intolerance to prior advanced therapy which includes biologics and targeted small molecules (advanced failures), and 2) patients who have demonstrated inadequate response to, loss of response to, or intolerance to prior conventional therapies (corticosteroids and/or immunosuppressants) but have not failed advanced therapy (conventional failures).

The study consists of a screening period of up to 35 days, a [REDACTED] treatment period, and a safety follow-up period for [REDACTED] following the final dose of study treatment. The induction period [REDACTED] will test the induction of clinical remission. After completion of the induction period, all patients, irrespective of clinical response or remission, will be eligible to continue study treatment during an optional active treatment

extension (ATE) period [REDACTED] During the ATE period, all patients will receive vixarelimab, including patients who received placebo during the induction period, and the durability of clinical response and remission will be explored.

Approximately 210 patients, including advanced failures and conventional failures, will be enrolled across global investigational sites. [REDACTED]

[REDACTED] Randomization will be stratified by previous advanced or conventional therapy failure and baseline modified Mayo Score (mMS) [REDACTED] Restrictions regarding concomitant therapy are outlined in Section 4.4.1.

Eligible patients will be randomized in a [REDACTED] ratio to one of the following treatment arms for the induction period ([REDACTED]):

- Vixarelimab [REDACTED] arm [REDACTED]
- Vixarelimab [REDACTED] arm [REDACTED]  
[REDACTED]
- Placebo [REDACTED] arm [REDACTED]

All patients who complete the induction period can receive SC injections of vixarelimab [REDACTED] during the optional ATE period [REDACTED]. Patients assigned to the vixarelimab [REDACTED] arm or vixarelimab [REDACTED] arm during the induction period will continue on their randomized treatment assignment during the optional ATE period:

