## **6.7 IMMUNOGENICITY ANALYSES**

The immunogenicity analysis population will consist of all patients with at least one postdose ADA assessment. Patients will be grouped according to treatment received or, if no treatment is received prior to study discontinuation, according to treatment assigned.

The numbers and proportions of ADA-positive patients and ADA-negative patients at baseline (baseline prevalence) and after drug administration (postbaseline incidence) will be summarized by treatment group. When determining postbaseline incidence, patients are considered to be ADA positive if they are ADA negative or have missing data at baseline but develop an ADA response following study drug exposure (treatment-induced ADA response), or if they are ADA positive at baseline and the titer of one or more postbaseline samples is at least 0.60 titer unit greater than the titer of the baseline sample (treatment-enhanced ADA response). Patients are considered to be ADA negative if they are ADA negative or have missing data at baseline and all postbaseline samples are negative, or if they are ADA positive at baseline but do not

[figure not shown]
have any postbaseline samples with a titer that is at least 0.60 titer unit greater than the titer of the baseline sample (treatment unaffected).

The relationship between ADA status and safety, efficacy, PK, and biomarker endpoints may be analyzed and reported via descriptive statistics.

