- o See Appendix 3. *The Mayo Score will be calculated by the Sponsor.*
- p Clinician-reported outcome instruments will be completed after the physical examination, prior to the administration of study treatment.
- q An electronic diary will be used to collect PRO data, including stool frequency/rectal bleeding and the UC-PRO/SS instrument (see Section 4.5.7.2). Stool frequency, rectal bleeding, and UC-PRO/SS will be collected daily over at least a 7-day period before each specified study visit.
- r On treatment days, all samples should be collected prior to dosing.
- s Additional ADA samples should be collected in patients with signs and symptoms of injection-related reactions.

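### The rule that leaves placebo patients' PK and postbaseline ADA samples unassayed does not end when they switch to vixarelimab and, with Section 6.7, also removes them from baseline ADA prevalence

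*Combined protocol and SAP*

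**What the plan says.** Section 4.2.2 (Blinding) sets the assay rule for placebo patients in two sentences. For drug concentration: "PK samples from patients assigned to the placebo arm will not be analyzed for study drug PK concentration except by request". For immunogenicity: "Postbaseline immunogenicity samples from patients assigned to the placebo arm will not be analyzed for ADAs except by request". Neither names a study period. The same section keeps one sample outside the rule: "Baseline immunogenicity samples will be analyzed for all patients". It also unblinds the PK and ADA laboratories to treatment assignment so that they can pick the samples to run.

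These patients do not stay on placebo if they continue. Section 3.1.1 says: "During the ATE period, all patients will receive vixarelimab, including patients who received placebo during the induction period". Section 4.2.1 agrees: "patients treated with placebo during the induction period will receive vixarelimab".

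Section 6.7 defines the immunogenicity population: "The immunogenicity analysis population will consist of all patients with at least one postdose ADA assessment". It names no other population and reports both baseline prevalence and postbaseline incidence by treatment group. Section 6.6 admits a patient to the PK population only with an evaluable vixarelimab concentration after dosing. Table 1 in Section 2 lists serum concentration at specified timepoints, baseline ADA prevalence and ADA incidence during the study as secondary endpoints, with no restriction to induction.

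**The concern.** A patient is assigned once, at randomization. Someone randomized to placebo is still assigned to the placebo arm after starting vixarelimab in the extension, so a laboratory that selects samples by assignment would set the on-drug samples aside. These patients are exposed for the first time in the extension, and it is there that their concentrations and any treatment-induced antibodies would appear.

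Two secondary endpoints would then be reported without an exposed group. The exploratory analyses relating exposure and ADA status to efficacy and safety would lose the same patients. If some samples are assayed on request, the likely triggers are an injection reaction or a suspected dosing error. ADA incidence among those tested would then not represent switched patients in general.

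The second consequence is smaller. Baseline samples from placebo patients are assayed, but without a postdose result these patients are outside the only population from which baseline prevalence is reported.

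**Working it through.** The plan gives no figure to reproduce on this point. The check compares the sections and then sizes the effect under stated assumptions.

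**Comparison of the text**

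- The trigger in Section 4.2.2 is the assigned arm. Sections 3.1.1 and 4.2.1 and Appendix 2 give the same patients vixarelimab in the extension. No visible passage restores default assaying at the switch.
- The protocol does add a period elsewhere: the dosing footnote in Appendix 2 refers to the placebo arm during induction. Section 4.2.2 has no such qualifier.
- The reason given in Section 4.2.2 is that "PK and ADA assay results for these patients are generally not needed for the safe conduct or proper interpretation of the study data". That holds while a patient is on placebo. It does not hold once the patient is on drug.
- Section 6.6 needs an evaluable concentration and Section 6.7 a postdose ADA assessment. If an assessment means an assayed result, placebo-assigned patients meet neither by default, whether or not they switch.

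**Size: inputs**

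- Total about 210 patients in three arms (Sections 4.2.1 and 6.1).
- Allocation ratio redacted. Assumed 1:1:1, or 2:2:1 with placebo the smaller arm.
- Extension entry by placebo patients not given. Assumed 70–90%.
- Baseline ADA prevalence not given. Assumed 5%.

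**Exposed patients without a default result**

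Switchers = placebo n × entry rate. Share = switchers / (active n + switchers).

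- 1:1:1: placebo n = 210 / 3 = 70, active n = 140.
  - 70% entry: 70 × 0.70 = 49; 49 / 189 = 26%.
  - 90% entry: 70 × 0.90 = 63; 63 / 203 = 31%.
- 2:2:1: placebo n = 210 / 5 = 42, active n = 168.
  - 70% entry: 42 × 0.70 = 29.4, about 29; 29.4 / 197.4 = 15%.
  - 90% entry: 42 × 0.90 = 37.8, about 38; 37.8 / 205.8 = 18%.

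**Precision of baseline prevalence**

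95% half-width = 1.96 × √(p(1 − p)/N), with p = 0.05, so 1.96 × √0.0475 = 0.4272.

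- N = 210: 0.4272 / √210 = 0.0295 (2.948 points, about 2.9).
- N = 140 (1:1:1): 0.4272 / √140 = 0.0361, about 3.6 points; √(210/140) = 1.22, so 22% wider.
- N = 168 (2:2:1): 0.4272 / √168 = 0.0330, about 3.3 points; √(210/168) = 1.12, so 12% wider.

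**The case against.** The best defence is that the rule was meant for induction only. Section 3.1.1 randomizes patients to arms for the induction period, the stated purpose of collecting placebo samples is to protect the blind, and Section 6.7 groups patients by treatment received. That is plausible as intent. No passage says it, however, and the laboratories are told to work from assignment.

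Several stronger readings are tempting, and the documents do not support them.

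- A reader might infer that testing is prohibited. It is not. Both sentences allow it on request, and results are said to be only generally unnecessary. Testing is off by default. Requests still do not amount to a planned analysis of all switched patients.
- A reader might infer that switched patients have no valid ADA baseline. They have one: the baseline sample is assayed for every patient and precedes any vixarelimab. What is missing by default is ADA status just before the switch.
- A reader might infer that ADA status after a reaction in a switched patient cannot be known. Appendix 2 says: "Additional ADA samples should be collected in patients with signs and symptoms of injection-related reactions". Appendix 5 asks for serum after suspected anaphylaxis. Neither excludes an arm, and a request would release the assay. Section 4.5.8 also allows residual PK and immunogenicity serum to be kept for up to 5 years after the final report. The gap is that nothing makes the assay the default.
- A reader might infer that Section 6.7 itself excludes placebo patients. It does not name them. The exclusion follows only from reading it with Section 4.2.2, and a placebo patient tested on request would be counted.

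It is also fair that no efficacy endpoint or induction comparison is touched, that both randomized vixarelimab arms are assayed by default, and that the exposure-response and ADA-relationship analyses are optional. The schedule grids are not shown and the Data Analysis Plan is a separate document, so extension sampling times and any later clarification cannot be checked.

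**Conclusion.** The concern holds as a default rule with no stated end. Followed as written, Section 4.2.2 leaves an exposed group without planned PK or ADA results, against secondary endpoints that are not confined to induction. The group is roughly 15–31% of all vixarelimab-exposed patients across the two assumed ratios and 70–90% extension entry. The true figure depends on the redacted ratio and the actual entry rate.

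The prevalence consequence is an inference from two sections. Baseline ADA is measured before treatment, so dropping one randomized arm costs precision rather than introducing bias: 0.4 to 0.7 points of half-width at the assumed 5%.

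The wording is wrong as it stands and should be corrected. The severity is moderate. A reader might take this as a flaw that must be repaired before the trial can be interpreted, but the documents do not support that, since the primary analysis and the randomized comparison are unaffected.

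**What to change.** In Section 4.2.2, limit both no-testing sentences to samples taken before the first dose of vixarelimab, and state that extension PK and ADA samples from patients who switched from placebo are assayed by default.

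In Section 6.7, replace the single population with two:

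- Baseline prevalence: all patients with a baseline ADA result.
- Postbaseline incidence: vixarelimab-treated patients with at least one ADA result after their first vixarelimab dose.

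State which pre-vixarelimab sample is the baseline for switched patients. The Day 1 sample is already assayed and can serve. Also assaying the last sample before the switch is optional; it would show ADA status immediately before first exposure.

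The cost is the wording and the assays on samples already collected. The laboratories are already unblinded to assignment, so blinding is not affected.

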### **4.3 STUDY TREATMENT AND OTHER TREATMENTS RELEVANT TO THE STUDY DESIGN**

The investigational medicinal product (IMP) for this study is vixarelimab.

[Appendix 6](#) identifies all investigational and non-investigational medicinal products for this study.

#### **4.3.1 Study Treatment Formulation and Packaging**

##### **4.3.1.1 Vixarelimab and Placebo**

Vixarelimab will be supplied by the Sponsor as sterile liquid in glass vials. For information on the vixarelimab formulation, see the pharmacy manual and Vixarelimab Investigator's Brochure.

Placebo will be supplied by the Sponsor as sterile liquid in glass vials indistinguishable from vials of blinded vixarelimab. For information on the placebo formulation, see the pharmacy manual.

### **4.3.2      Study Treatment Dosage, Administration, and Compliance**

The treatment regimens are summarized in Section [3.1.1](#).

Refer to the pharmacy manual for detailed instructions on drug preparation.

Details on treatment administration (e.g., dose and timing) should be noted on the Study Drug Administration electronic Case Report Form (eCRF). Cases of accidental overdose or medication error, along with any associated adverse events, should be reported as described in Section [5.3.6](#).

Guidelines for treatment interruption or discontinuation for patients who experience adverse events are provided in Section [5.1.2](#).

#### **4.3.2.1      Vixarelimab and Placebo**

Vixarelimab and matching placebo will be administered by SC injection.

Patients assigned to vixarelimab [REDACTED] arm will receive [REDACTED] vixarelimab at [REDACTED] throughout the induction period and optional ATE period. Patients assigned to vixarelimab [REDACTED] will receive [REDACTED] vixarelimab [REDACTED] throughout the induction period and optional ATE period. [REDACTED], patients assigned to vixarelimab [REDACTED] will also receive [REDACTED] through the induction period and optional ATE period. Patients assigned to placebo [REDACTED] [REDACTED] in the induction period and [REDACTED] vixarelimab [REDACTED] in the optional ATE period. Study treatment should be administered after all other procedures have been completed at each visit, unless specifically indicated otherwise.

Administration of study treatment will be performed at the clinical site by trained personnel in a monitored setting where there is immediate access to adequate equipment and medications (e.g., IV solutions, epinephrine, antihistamines, corticosteroids) to manage potentially serious reactions.

Patients should be monitored during study treatment [REDACTED]  
[REDACTED]

Investigators and healthcare professionals administering study treatment should recognize and manage the signs and symptoms of anaphylactic reactions according to 2006 National Institute of Allergy and Infectious Disease/Food Allergy and Anaphylaxis Network guidelines (Sampson et al. 2006; [Appendix 8](#)). Healthcare professionals should also instruct patients on how to recognize the symptoms of any such events and to contact a healthcare provider or seek emergency care in case of any such symptoms. All cases of suspected allergic or anaphylactic reactions will be documented through the

Anaphylaxis, Anaphylactoid, and Hypersensitivity Reaction eCRF. For anaphylaxis precautions, see [Appendix 5](#).

Rules for treatment interruption are provided in Section [5.1.2.2](#). Dose modifications are not permitted.

#### **4.3.3 Investigational Medicinal Product Handling and Accountability**

All IMPs required for completion of this study will be provided by the Sponsor. The study site (i.e., investigator or other authorized personnel [e.g., pharmacist]) is responsible for maintaining records of IMP delivery to the site, IMP inventory at the site, IMP use by each patient, and disposition or return of unused IMP, thus enabling reconciliation of all IMP received, and for ensuring that patients are provided with doses specified by the protocol.

The study site should follow all instructions included with each shipment of IMP. The study site will acknowledge receipt of IMPs supplied by the Sponsor, using the IxRS to confirm the shipment condition and content. Any damaged shipments will be replaced. The investigator or designee must confirm that appropriate temperature conditions have been maintained during transit, either by time monitoring (shipment arrival date and time) or temperature monitoring, for all IMPs received and that any discrepancies have been reported and resolved before use of the IMPs. All IMPs must be stored in a secure, environmentally controlled, and monitored (manual or automated) area in accordance with the labeled storage conditions, with access limited to the investigator and authorized staff.

Only patients enrolled in the study may receive IMPs, and only authorized staff may supply or administer IMPs.

IMPs will either be disposed of at the study site according to the study site's institutional standard operating procedure or be returned to the Sponsor with the appropriate documentation. The site's method of destroying Sponsor-supplied IMPs must be agreed to by the Sponsor. The site must obtain written authorization from the Sponsor before any Sponsor-supplied IMP is destroyed, and IMP destruction must be documented on the appropriate form.

Accurate records of all IMPs received at, dispensed from, returned to, and disposed of by the study site should be recorded on the drug accountability log.

Refer to the pharmacy manual and/or the Vixarelimab Investigator's Brochure for information on IMP handling, including preparation and storage, and accountability.

#### **4.3.4 Continued Access to Vixarelimab**

Currently, the Sponsor (Genentech, a member of the Roche Group) does not have any plans to provide Genentech IMP (vixarelimab) or any other study treatments to patients

who have completed the study. The Sponsor may evaluate whether to continue providing vixarelimab in accordance with the Roche Global Policy on Continued Access to Investigational Medicinal Product, available at the following website:

[https://assets.cwp.roche.com/f/176343/x/92d6b13ee6/policy\\_continued\\_access\\_to\\_investigational\\_medicines.pdf](https://assets.cwp.roche.com/f/176343/x/92d6b13ee6/policy_continued_access_to_investigational_medicines.pdf)

